7. ADHERENCE

With a total of 9 physical activity coaching intervention sessions, a minimum of 6 sessions must be attended to be included for data analysis. Accelerometer wear time must exceed 600 min/day over 4 days to be included as a measure of physical activity for any given time point.

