Research Design: This study will employ a multi-centre, randomized, wait-list controlled trial. A total of 30 participants (15 experimental, 15 wait-list control) between 18-65 years of age who have chronic $SCI \ge 1$ year prior will be recruited. Physical activity measures will be taken using wrist-based accelerometers and the Physical Activity Recall Assessment for Persons with SCI. Psychosocial factors will be evaluated through questionnaires. The primary health outcome measure (aPWV), and secondary cardiovascular parameters will be assessed using a combination of echocardiography and ultrasound. Fitness will be determined using a peak oxygen consumption test on an armcycle ergometer. All measurement will be taken at baseline and after 9 weeks following intervention commencement. Physical activity will also be sampled mid-intervention at 4 and 7 weeks. For the wait-list control group, an additional measurement time point will be added after they have received the intervention upon completion of the control period. Training will involve weekly, 10-15 minute coaching sessions for 9 weeks. All pre- and post-assessments will take place at the Blusson Spinal Cord Centre at ICORD or the University of British Columbia Okanagan. Intervention content will be delivered over Skype or phone, and the wrist- worn accelerometers will be delivered and picked up from the participant's home during the intervention.

Statistical Analyses: Analyses will be conducted to determine the training (time), group (control vs experimental) and interaction (time x group) of all indices.

Table of Contents

SUN	/IMARY	. 2
Prea	amble	. 5
1.	BACKGROUND AND PROGRAM RATIONALE 1.1 Physical inactivity and spinal cord injury (SCI) 1.2 Physical inactivity and cardiovascular disease (CVD) in spinal cord injury (SCI) 1.3 The Health Action Process Approach and physical activity interventions in spinal cord injury.	5 5 5 d 6
2.	PURPOSE & HYPOTHESES	. 6
3.	RESEARCH DESIGN/ PROTOCOL	. 7
4.	RECRUITMENT	. 9
5.	OUTCOME MEASURES	10
Pi	rimary Outcome Measure: Physical activity 6.1.1: Physical Activity Recall Assessment for People with Spinal Cord Injury (PARA- SCI):	10 .10 .10
	6.1.2: 6-day Physical Activity Monitoring Period	10
	Measurement of energy expenditure during different sub-maximal wheeling speeds for calculation of moderate-vigorous physical activity during the 6-day physical activity	
	monitoring period	11

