3. RESEARCH DESIGN/ PROTOCOL

A multi-centre, randomized, wait-list controlled trial will be used to compare the effects of tailored PA coaching sessions *versus* no coaching on PA behaviour, psychosocial factors, and health outcomes. Eligible individuals will be randomly assigned (1:1) to either the experimental (PA coaching sessions) or wait-list control condition. Groups will be stratified by injury level, age, and site. The randomization sequence will be generated by a research assistant independent of the trial. For an overview of the protocol see Figure 1.

Figure 1. Study Overview

Day 1 testing measures include vascular measures (arterial pulse wave velocity, arterial structure, and flow mediated dilation; 30 minutes), cardiac structure and function measures (30 minutes), administration of the demographics and Health Action Process Approach model questionnaire (25 minutes), and a measurement of energy expenditure at different sub-maximal wheeling speeds to calibrate MVPA cut-points (35 minutes) for a total duration of 2 hours. Participants will be given an accelerometer to wear for the 6-day monitoring period (6.1.2) after which they will return for Day 2 testing.

Day 2 testing measures include administration of the PARA-SCI (45 minutes), a peak oxygen uptake test (45 minutes), and at baseline, the first PA coaching session will be

administered (30 minutes) whereas at post-test a semi-structured interview will be administered (30 minutes). Total duration of day 2 testing will be 2 hours. The intervention protocol is described below. During the intervention, physical activity will be sampled at two time points; accelerometer and PARA SCI data will be taken during week 4 and week 7. Following the intervention, follow-up assessments of physical activity will be sampled monthly for 12 months in the intervention group only using the Leisure Time Physical Activity Questionnaire.

INTERVENTION

Intervention Protocol:

Experimental participants will receive weekly PA coaching sessions. Each session will be 10-15 minutes in duration and delivered either face to face, over Skype, or when the former modes are unavailable, over the phone. These sessions will be recorded using a portable audio recorder. Additionally, supplemental resources may be emailed to the participants based on need throughout the intervention.

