Control participants will complete baseline and post-testing only. Following completion of post-test measures they will be administered the same PA coaching session as the intervention group, with post-test measures being repeated upon intervention completion.

Standardization across sites

The intervention will take place in Vancouver for the months of April to July and in Kelowna from August to October. The same equipment brand and model will be used between sites where available. All intervention content, psychological, and fitness measures will be delivered by the same researcher. Although vascular and cardiac measures will be administered by different researchers in Vancouver and Kelowna, all technicians are experienced in their respective techniques, decreasing the likelihood of human error.

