4. RECRUITMENT

A total of 30 participants with a chronic (>1 year post injury) spinal cord injury between 18-65 years of age will be recruited. Individuals must be competent to give informed consent, and be able to propel an arm ergometer.

Exclusion Criteria:

- History and/or symptoms of CVD or cardiopulmonary problems/disease.
- Major trauma or surgery within the last 6 months.
- Active Stage 3 or 4 pressure ulcer (based on the National Pressure Ulcer Advisory Panel classification)
- Recent (within 1 year) history of lower-extremity or non-union fracture
- Any unstable medical/psychiatric condition or substance abuse disorder that is likely to affect their ability to complete this study.
- Individuals with active medical issues such as pressure sores, urinary tract infections, hypertension, or heart disorders.
- Any cognitive dysfunction or language barrier that would prevent subjects from following English instructions.
- Subjects may be excluded at the discretion of the principal investigator due to other, unforeseen, safety issues.

Sample size calculation: Our study is powered to detect a significant condition X time effect for our primary outcome measure, min/wk of PA. A previous single-group study of adults with SCI tested the effects of a PA-enhancing intervention delivered by a peer and a fitness trainer (Latimer-Cheung et al., 2013). That study found very large, significant effects for change in min/wk of PA (d = .96). Given our two-group design, we are powering for a more modest interaction effect (d = .75). Twelve participants/condition (N = 24) are needed to yield a significant effect of this magnitude in a repeated measures ANOVA, with $\beta = .80$ and $\alpha = .05$. To account for study dropouts, we are budgeting for an N of 30.

Potential participants will be identified through a variety of recruitment strategies including: posters which will be distributed among hospital locations and local community venues (e.g. local sports venues, community program centres); social media advertising (i.e., website, Facebook, Twitter); email; and at the individual's request (some participants have previously provided consent to be contacted for future studies).

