8. DATA ANALYSIS

To test hypothesis i, differences in physical activity levels will be examined using repeated measures analyses of covariance with baseline physical activity as the covariate. Where significant intervention x time interactions are found, post-hoc analyses will be conducted to determine the specific time point at which differences in physical activity between groups are found.

To test hypothesis ii, independent samples t-tests will compare post-intervention HAPA model constructs between groups.

To test hypothesis iii, we will use separate hierarchical regressions with change in physical activity entered as the predictor of change in arterial stiffness and secondary

health outcomes (cardiovascular, fitness).

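### The 6-of-9 session rule, on its natural reading, drops only experimental participants from the randomised comparison for hypotheses i and ii, and no all-randomised analysis is stated

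*Combined protocol and SAP*

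**What the plan says.** Section 7 (Adherence) sets the rule: out of nine sessions, "a minimum of 6 sessions must be attended to be included for data analysis". It names no arm or hypothesis and does not describe the resulting set as a sensitivity set. The wear-time rule beside it is separate: it applies to each time point in either arm.

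Section 3 (Research Design/Protocol) describes the comparison: "Eligible individuals will be randomly assigned (1:1) to either the experimental (PA coaching sessions) or wait-list control condition". On controls it says "Control participants will complete baseline and post-testing only", and then "Following completion of post-test measures they will be administered the same PA coaching session as the intervention group".

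Section 8 (Data Analysis) tests hypothesis i by "repeated measures analyses of covariance with baseline physical activity as the covariate" and adds "Where significant intervention x time interactions are found, post-hoc analyses will be conducted". Hypothesis ii is tested by independent t-tests on post-intervention scores, without baseline adjustment. Neither test has a stated analysis population or missing-data method, and no all-randomised or intention-to-treat analysis appears elsewhere.

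The only allowance for loss is in Section 4 (Recruitment), where 24 is raised to 30: "To account for study dropouts, we are budgeting for an N of 30".

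**The concern.** During the compared period only experimental participants have sessions to miss. If low attenders are removed from that arm, their counterparts among the controls cannot be identified and stay in, so the arms are no longer those that randomisation produced.

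A link between attendance and outcome is plausible in either direction. Section 3 enrols people at different motivational stages. If the less motivated attend less, excluding them favours coaching. If people who are already active skip sessions, excluding them works against it. With 15 per arm, each exclusion is 1/15, or about 7%, of the experimental arm. Because this is the only analysis set stated, a reader of the results could not tell whether such bias had occurred.

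Hypothesis iii is not a comparison of randomised arms and is outside this point.

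**Working it through.** **1. Possible readings of the rule.**
- Applied to everyone at post-test, it would exclude every control (0 sessions attended). That cannot be intended.
- Applied to controls through their later coaching, it would select them on behaviour after the compared outcome was measured. That is still not an all-randomised analysis.
- Applied to experimental participants only, it selects one arm. This is the natural reading.

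**2. Inputs for an illustration.** The documents give 15 per arm. They give no attendance rate. The dropout allowance is (30 − 24)/2 = 3 per arm; it is not an attendance figure, but it makes 3 of 15 a reasonable middle case, with 1 and 5 either side. Assumed: no true effect, and correlation r between attendance and outcome of .3 to .5. The plan has no figure of its own to reproduce here.

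**3. Hypothesis ii (unadjusted t-test).** With the k lowest attenders of 15 removed, bias in SD units = r × m_k, where m_k is the expected mean of the top 15 − k of 15 standard normal values: m_1 = .124, m_3 = .328, m_5 = .516. Type I error is by simulation.

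| Excluded | Bias, r = .3 | Bias, r = .5 | Type I error, r = .3 to .5 |
|---|---|---|---|
| 1 | .3 × .124 = .04 | .5 × .124 = .06 | .05–.06 |
| 3 | .3 × .328 = .10 | .5 × .328 = .16 | .06–.07 |
| 5 | .3 × .516 = .15 | .5 × .516 = .26 | .07–.10 |

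With r = 0 the bias is 0 and the error rate stays at .05. With r = −.3 the biases are −.04, −.10 and −.15.

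**4. Hypothesis i (baseline-adjusted).** Take a week-9 ANCOVA, with an assumed correlation of .6 between baseline and week-9 activity. The bias is approximately (r_outcome − .6 × r_baseline) × m_k.
- Attendance related to outcome only through baseline (r_outcome = .6 × r_baseline): bias 0, type I error .05.
- Attendance equally related to both: the multiplier is .4r. Simulated bias is about .02–.03, .04–.07 and .06–.11 SD for 1, 3 and 5 excluded; type I error is at most about .06.
- Attendance unrelated to baseline: bias as in step 3; type I error about .05–.06, .06–.08 and .07–.12.

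The last case is extreme. At r = .5, attendance correlates .5/√(1 − .36) = .5/.8 = .625 with baseline-adjusted activity, although coaching is assumed to do nothing.

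If both arms have weeks 4, 7 and 9 and the intervention x time interaction is the test, type I error stays at .05 when selection is constant over time. If selection grows (0, half and full correlation at weeks 4, 7 and 9), it is .05, .06–.07 and .06–.09.

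**5. Power cost of including everyone.** In a plain t-test, d = .75 at 12 per arm gives power .42, so the plan's claimed .80 depends on a correlation that it does not state. Solving instead for .80 at 12 per arm gives a standardised effect of 1.197. With that effect, and low attenders who gain nothing:

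| Low attenders | Current rule (excluded) | All randomised |
|---|---|---|
| 1 | 14 v 15: .87 | .83 |
| 3 | 12 v 15: .84 | .67 |
| 5 | 10 v 15: .80 | .50 |

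The right-hand column is simulated and includes the extra variance from mixing people who gain with people who do not. The middle column assumes no selection bias.

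**The case against.** The best defence is that the harm is unproven and may be slight. With one exclusion the effect is small. Baseline adjustment can remove the hypothesis i bias entirely. The sample size is framed on a condition x time effect and Section 8 hangs its post-hoc tests on that interaction, which holds .05 when selection is constant. All of this stands, and it limits what can be said about size. It does not supply the missing analysis set, and it does not help hypothesis ii, which has no baseline adjustment. Nor is the interaction a full shield: hypothesis i is worded as a difference in levels, and selection that grows over time affects the interaction too.

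A second objection is that including non-attenders lowers power, which is true. But the power kept by exclusion belongs to a comparison that is no longer between the randomised arms.

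Two stronger readings are tempting. A reader might infer that the plan is biased in favour of coaching; the documents do not show the direction. A reader might also infer that the primary test's type I error could reach about .18. That figure comes from a group main effect over weeks 4, 7 and 9 with 5 excluded. It needs control data at weeks 4 and 7, which Section 3's paragraph on controls does not support, and a main effect that Section 8 does not separately name. It also needs an extreme correlation: the baseline-adjusted three-week mean has SD √(.733 − .36) = .611, where .733 = (1 + 2 × .6)/3, so attendance would correlate .5/.611 = .82 with it.

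**Conclusion.** The structural point holds with high confidence. As written, the plan conditions inclusion on attendance, only the experimental arm has sessions to attend before post-test, and no all-randomised analysis is stated for hypotheses i and ii.

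Confidence in the size is low. Every figure above rests on an assumed number of exclusions and an assumed correlation. Within those assumptions, the hypothesis ii type I error runs from about .05 to .10. For hypothesis i the effect runs from none to about .12–.13, the top end being the extreme week-9 case with 5 excluded. The point deserves correction because the rule governs the primary hypothesis and the set should be fixed before outcomes are analysed, not because a large bias has been demonstrated.

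**What to change.** In Section 8, add: *The primary analysis of hypotheses i and ii includes all randomised participants in their assigned arm, regardless of sessions attended. Week-9 measures are sought from everyone, including low attenders, and participants with missing outcomes are reported by arm.*

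In Section 7, replace the rule with: *The 6-of-9 attendance criterion defines a per-protocol sensitivity analysis, labelled as such.* The wear-time rule may stay as a data-validity rule for each time point.

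Also reconcile the Summary ("Physical activity will also be sampled mid-intervention at 4 and 7 weeks") with Section 3's paragraph on controls, so that it is clear whether controls have activity measures at weeks 4 and 7. Without them, hypothesis i reduces to a week-9 comparison between arms.

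A likelihood-based mixed model for hypothesis i and imputation for hypothesis ii are optional.

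Cost: a few sentences, no new visits, and effort to bring low attenders back at week 9. That effort matters, because if they also miss week 9 bias remains. With 3 missing, r = .5 and no relation to baseline, an available-case analysis is biased by about .17 SD, much as under exclusion; a likelihood-based model using earlier activity data about halves this (.09 to .10 SD). The real downside is the dilution and loss of power in step 5 of the working. The diluted estimate is the effect of offering coaching, which is what the randomised comparison estimates.

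### The repeated-measures ANCOVA has no rule for invalid accelerometer time points; analysed complete-case, it discards valid data and draws on a margin budgeted only for dropouts

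*Combined protocol and SAP*

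**What the plan says.** - **Wear rule.** Section 7 (Adherence): "Accelerometer wear time must exceed 600 min/day over 4 days to be included as a measure of physical activity for any given time point". The rule removes a time point, not a participant.
- **Outcome affected.** Section 6.1.2 names accelerometer minutes per day at moderate intensity or above as the primary outcome. The PARA-SCI recall (6.1.1) sits under the same primary-outcome heading and has no wear rule.
- **Analysis.** Section 8 (Data Analysis), hypothesis i: "differences in physical activity levels will be examined using repeated measures analyses of covariance with baseline physical activity as the covariate". Post-hoc comparisons then locate the time point at which the arms differ, so more than one post-baseline time point is expected in the model. No imputation, estimation method or other missing-data rule is given.
- **Sample size.** Section 4 (Recruitment): "Twelve participants/condition (N = 24) are needed to yield a significant effect of this magnitude in a repeated measures ANOVA", and then "To account for study dropouts, we are budgeting for an N of 30". No dropout rate is given, and nothing is added for invalid wear.
- **Time points.** The Summary and Section 3 place activity measurement at baseline, weeks 4 and 7, and 9 weeks. Under Control Participants, Section 3 says "Control participants will complete baseline and post-testing only".

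**The concern.** A classical repeated-measures ANCOVA works on complete rows: the covariate and every repeated value must be present. A participant who under-wears the device in week 4 would then lose a valid week-9 result as well. The wear rule is mild in itself, but with this method its effect multiplies across time points.

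Three things are at stake in a 30-person trial. Valid primary-outcome data are thrown away. Power falls. The comparison is restricted to people who wore the device well every time, who may be the more engaged participants. The only reserve is six people, and dropouts already have a claim on it. So does the separate rule in Section 7 that at least 6 of 9 sessions be attended.

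**Working it through.** **The plan's own figures.** The 24 cannot be checked from the stated inputs, because the number of measurements and their correlation are not given. Take d = 0.75 as f = d/2 = 0.375 and a within-between interaction test at alpha 0.05. Then 24 is the smallest even N that reaches 80% power with, for example, 2 measurements and correlation 0.25 (power 0.818), or 3 measurements and correlation 0.1 (power 0.835). The margin is 30 - 24 = 6, or 6/30 = 20%, and 24/(1 - 0.20) = 30. Seven losses are needed to fall below 24.

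**Assumption.** The documents give no rate of invalid time points. Call it q per time point, independent across time points, with no other loss.

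**Expected complete cases**, with k time points required: 30 x (1 - q)^k. The chance of fewer than 24 is binomial.

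| q | k = 4 (baseline, weeks 4, 7, 9) | P(fewer than 24) | k = 2 (baseline, post-test) | P(fewer than 24) |
|---|---|---|---|---|
| 2% | 27.7 | 0.007 | 28.8 | 0.000 |
| 5% | 24.4 | 0.32 | 27.1 | 0.02 |
| 10% | 19.7 | 0.93 | 24.3 | 0.34 |
| 15% | 15.7 | 0.998 | 21.7 | 0.77 |

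**Break-even.** Setting 30 x (1 - q)^k = 24 gives q = 1 - 0.8^(1/k):
- k = 4: 1 - 0.8^(1/4) = 5.4%
- k = 2: 1 - 0.8^(1/2) = 10.6%

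If three people have already been lost, the starting number is 27 and q = 1 - (24/27)^(1/k): 2.9% for k = 4 and 5.7% for k = 2.

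**What complete-case handling costs.** Simulated power, assuming 15 per arm, d = 0.75, correlation 0.6 between all time points and the same effect at weeks 4, 7 and 9, for q = 5%, 10% and 15%:
- Week-9 contrast: about 59%, 45% and 36% with complete cases, against 66%, 57% and 54% using all valid time points.
- Contrast averaged over time: about 82%, 68% and 56%, against 87%, 82% and 81%.

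With no invalid wear at all, the week-9 contrast has about 70% power under these assumptions. Only the gap within each pair is therefore due to how invalid time points are handled. Neither contrast is the planned arm-by-time test, so these figures show the direction and rough size of the loss. They are not the trial's power.

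**The case against.** **Deletion is inferred.** Neither section mentions dropping participants. Section 7 removes a time point only, and a likelihood-based repeated-measures fit would keep the rest. This stands as a limit on the claim. However, complete-case analysis is how the named method works in its classical form, and nothing in the plan points to another form.

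**Invalid wear may be rare.** Section 6.1.2 provides reminders, home delivery and pick-up of the device, and 24-hour wear for 6 days when only 4 qualifying days are needed. At 2% invalid, the expected sample is 27.7. This also stands: a reader might infer that the analysed sample will fall below 24, but the documents give no rate that would support it.

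**Below 24 is not the same as underpowered.** This is correct. With 2 measurements and N = 20, the interaction test has power 0.887 at correlation 0.5 and 0.708 at correlation 0.2, and the plan states no correlation.

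**A week-9 test could cost more than deletion does.** If the effect is constant over time, the time-averaged complete-case comparison has more power than a week-9 contrast. That argues against moving the hypothesis test to week 9. It does not argue against using all valid data.

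**Conclusion.** The concern holds as a gap in the primary analysis that should be closed. The plan voids individual time points, names a method that classically needs complete rows, and gives no rule connecting the two. Under complete-case handling, the whole six-person margin is expected to be used up at about 5.4% invalid time points with four in the model, or 10.6% with two. Both figures assume independent invalid time points and no dropouts or session exclusions; any such loss lowers them. The point applies to the accelerometer outcome and not to PARA-SCI.

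A reader might also infer that a complete-case model would keep no control participant, because controls are said to have only baseline and post-test data. The documents do not support this. On that reading the between-group model can contain only those two time points, and the two-time-point counts apply. The four-time-point counts apply only if controls are also sampled at weeks 4 and 7. What the documents do show is that the two descriptions of control sampling disagree.

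**What to change.** 1. In Section 8 (Data Analysis), replace the repeated-measures ANCOVA for hypothesis i with a linear mixed model for repeated measures (REML, small-sample degrees of freedom), with arm, time, arm-by-time and baseline activity, using all valid post-baseline time points.
2. Keep the wear rule at time-point level, and say that an invalid time point does not remove the participant.
3. State how an invalid baseline is handled, since a baseline covariate alone would still drop those people. Either move baseline into the outcome vector with a mean common to both arms, in place of the covariate, or keep the covariate with a stated imputation.
4. Keep the planned arm-by-time test and report the arm contrast at each time point. The test need not move to week 9.
5. Reconcile the Control Participants text in Section 3 with the week-4 and week-7 sampling in the Summary and Section 3, so that the time points in the between-group model are clear.

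The cost is analysis wording and standard software, with no new data. There is a small downside: the model relies on a missing-at-random assumption and estimates a covariance structure from about 30 people, so a simple structure should be prespecified. The session-attendance rule is a separate exclusion that this change does not touch.
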